11.5.3 Questionnaire on dosage form

Investigator will ask Question 1 and Question 2 regarding the patch dosage form of antipsychotic, Question 3 regarding the DSP-5423P, and record the assessment Date and the results to CRFs.

- Would you like the patch dosage form to be available??

Response) "Yes" or "No"

- Is it easy for you to continue treatment with patches compared with tablets?

Response) "Yes," "Equal" or "No."

- Question 3 Would you like to use the patches that you used during this study in the future?

Response) "Yes" or "No"

12. SAFETY REPORTING

12.1 Definition

12.1.1 Adverse events

An adverse event (AE) is any untoward medical occurrence in a study subject administered a medicinal (investigational) product and which does not necessarily have a causal relationship with this treatment. An AE can, therefore, be any unfavorable and unintended sign (including an abnormal laboratory finding), symptom, or disease occurring after the administration of a medicinal (investigational) product, whether or not considered related to the medicinal (investigational) product. AEs may include the onset of new illness and the exacerbation of pre-existing conditions. AEs will be collected from the beginning of the study treatment in the washout phase until the follow-up visit.

AEs also include other untoward events occurring from the beginning of the DSP-5423 (tablet) administration until the follow-up visit in the cohort 1, or from the beginning of the DSP-5423P application until the follow-up visit in the cohort 2, for instance, events occurring in association with study-related procedures or assessments, or those occurring under placebo treatment.

In the cohort 1. AEs that occur during the DSP-5423 (tablet) administration period and worsen during the DSP-5423P application period will be recorded as AEs in the DSP-5423 (tablet) administration period and also as AEs in the DSP-5423P application period. The date of worsening will be recorded as the onset date of the worsening AE. In addition, AEs that occur during the DSP-5423 (tablet) administration period without further worsening in the DSP-5423P application period will be recorded as AEs in the DSP-5423 (tablet) administration period.

Lack of efficacy may be an expected potential outcome and should not be reported as an AE unless the event is unusual in some way. New signs and symptoms of the underlying disease, or signs and symptoms of an emerging disease should be recorded as AEs.

The Investigator should attempt to establish a diagnosis of the event based on signs, symptoms, and/or other clinical information. In such cases, the diagnosis should be recorded as the AE and not the individual signs/symptoms.

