12.1.2 Serious adverse events

A serious adverse event (SAE) is an AE that meets one or more of the following criteria:

- Results in death.

- Is life-threatening (ie, a subject is at immediate risk of death at the time of the event, not an event where occurrence in a more severe form might have caused death).
- Requires hospitalization or prolongation of existing hospitalization.
- Results in persistent or significant disability or incapacity.
- Is a congenital anomaly or birth defect.
- Is an important medical event that may jeopardize the subject or may require a medical or surgical intervention to prevent one of the outcomes listed above. Examples of such medical events include allergic bronchospasm requiring intensive treatment in an emergency room or at home, blood dyscrasias or convulsions that do not result in inpatient hospitalization.

The term "severe" is often used to describe the severity of a specific event (as in mild, moderate, or severe myocardial infarction) (see Section 12.3); the event itself, however, may be of relatively minor medical significance (such as severe headache). This is not the same as "serious," which is based on subject/event outcome or action criteria usually associated with events that pose a threat to a subject's life or functioning as defined by the criteria above.

During the study, if a subject has a hospitalization or procedure that was scheduled before the study entry, ie, before informed consent for an event/condition that occurred before the study, the hospitalization is considered a therapeutic intervention and not the result of a SAE. However, if the event/condition worsens during the study, it should be reported as an AE (or SAE, if the event/condition results in a serious outcome such as prolongation of hospitalization).

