13. TERMINATION OF SUBJECT FROM STUDY/DISCONTINUATION OF STUDY DRUG

13.1 Criteria for Subject Termination

Subjects may terminate the study participation at any time for any reason.

The possible reasons for the termination of study participation are as follows:

- Adverse event
- Suicide ideation
- Study drug discontinuation
- Lack of efficacy
- Lost to follow-up
- Pregnancy
- Withdrawal by subject
- Failure to apply >50% of the study medication since the last visit
- Protocol violation
- Other

If at any time during the course of the study, in the opinion of the Investigator, the subject may no longer safely participate due to a change in medical status (eg, experiences an AE or suicide ideation, becomes pregnant), or discontinuation of the study drug should be considered, the subject must be discontinued from the study treatment.

The date of discontinuation and the reason for discontinuation will be recorded in the appropriate CRF. Subjects who prematurely terminate the study participation will not be replaced.

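### Protocol 12.1.1 does not settle whether a hospitalised worsening of existing schizophrenia symptoms is an adverse event, so the same admission can be a 24-hour SAE at one site and only lack of efficacy at another.

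*Protocol*

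**What the plan says.** Three sentences in Protocol 12.1.1 bear on worsening of schizophrenia during the study.

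- First paragraph: "AEs may include the onset of new illness and the exacerbation of pre-existing conditions". Nothing excepts the disease under study.
- Fourth paragraph: "Lack of efficacy may be an expected potential outcome and should not be reported as an AE unless the event is unusual in some way". Unusual is not defined.
- Same paragraph, next sentence: "New signs and symptoms of the underlying disease, or signs and symptoms of an emerging disease should be recorded as AEs".

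Protocol 12.1.2 then builds seriousness on top of the AE definition: "A serious adverse event (SAE) is an AE that meets one or more of the following criteria". One criterion is "Requires hospitalization or prolongation of existing hospitalization". Protocol 12.4.1 requires SAEs to reach the sponsor within 24 hours of the investigator's awareness. Protocol 13.1 lists adverse event and "Lack of efficacy" as separate possible termination reasons and gives no rule for choosing between them.

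SAP 7.2.1 repeats the general AE definition. SAP 9.12.1 tabulates serious TEAEs and TEAEs leading to discontinuation from what the sites recorded as AEs.

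**The concern.** The boundary falls on a foreseeable event. Protocol 4.1 describes schizophrenia as a relapsing disease, prior antipsychotics are withdrawn before study drug starts, and 10.3.3.1 provides rescue antipsychotics for urgent psychiatric symptoms. Because relapse is characteristic of the disease, an investigator can reasonably decide that a given episode is not unusual.

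Two things are at stake. The first is prompt safety reporting: the sponsor may hear of some relapse admissions within 24 hours and not of others. The second is the safety summary itself. The primary objective is the 52-week safety of the patch, and the serious-TEAE and TEAE-leading-to-discontinuation rates would depend partly on which sentence of 12.1.1 a site applied. The study has no control arm, so there is no comparison group subject to the same recording practice against which such an error could be judged.

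**Working it through.** The plan states no figure on this point, so the check is a reading of the text. Take one hypothetical case: during the patch period a subject's existing hallucinations and agitation worsen, rescue antipsychotic is given, the subject has an unplanned admission, and study drug is stopped.

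| Step | Site A: exacerbation | Site B: lack of efficacy |
|---|---|---|
| AE under 12.1.1? | Yes, first paragraph | No, fourth paragraph: not judged unusual, and the symptoms are not new |
| SAE under 12.1.2? | Yes, hospitalisation criterion | No, because there is no AE to be serious |
| 24-hour report under 12.4.1? | Yes | Not triggered |
| Termination reason under 13.1 | Adverse event | Lack of efficacy |
| Serious-TEAE table, SAP 9.12.1 | Counted | Absent |
| TEAE leading to discontinuation, SAP 9.12.1 | Counted | Absent |

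Both columns follow the text. I then looked for a provision elsewhere that would decide between them.

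1. **Hospitalisation carve-out in 12.1.2.** The statement that "the hospitalization is considered a therapeutic intervention and not the result of a SAE" applies to admissions scheduled before consent. The sentence that follows, "However, if the event/condition worsens during the study, it should be reported as an AE", is tied to that same situation. Neither reaches an unplanned admission for relapse.
2. **Protocol 13.1.** It lists possible reasons and does not assign relapse to any of them.
3. **SAP 7.2.1 and 9.12.1.** They contain no rule on lack of efficacy, exacerbation or relapse.
4. **SAP 9.1 and 9.11.4.** The disposition categories name no reasons for discontinuation, and time to discontinuation counts all causes. Neither analysis isolates relapse withdrawals.

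**Where the episode would still appear at Site B.** The discontinuation date and reason are in the CRF (13.1) and in the listing of discontinued subjects (SAP 9.1). The rescue antipsychotic is recorded with dates, reason and daily dose (10.3). PANSS and CGI-S are rated before other antipsychotics are started after study treatment (11.2.1, 11.2.2). None of these starts the 24-hour clock or feeds a TEAE table.

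**Size.** Let h be the proportion of patch-treated subjects admitted for worsening of persisting symptoms, and f the share of those read as lack of efficacy. The serious-TEAE rate is then understated by at most h × f; it is less if some of those subjects have another serious TEAE. The documents give neither h nor f. Purely as assumed values:

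| h (assumed) | f = 0 | f = 0.5 | f = 1 |
|---|---|---|---|
| 5% | 0 | 2.5 points | 5 points |
| 10% | 0 | 5 points | 10 points |
| 20% | 0 | 10 points | 20 points |

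This shows how the rate depends on the reading. It is not an estimate for this trial.

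**The case against.** The strongest reply is that worsening and failure to respond are different things. Read together, the sentences can mean that non-response is not an AE while deterioration may be one. The general definition of an AE as any untoward occurrence, the hospitalisation criterion and the exception for unusual events all lean towards reporting an admission. An SAP is also not where AE reporting rules normally sit, so its silence is weak evidence. Much of this stands, and it rules out several stronger readings.

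- **That 12.1.1 contradicts itself.** The exacerbation sentence is permissive, so this is an unresolved boundary. Permissive wording still allows sites to differ.
- **That the fourth paragraph limits recording to new symptoms.** It has no limiting word and, if anything, widens recording. A relapse with newly emerged symptoms is already an AE, and an SAE if the subject is admitted. Only worsening of persisting symptoms lacks a rule.
- **That the event goes unreported altogether.** It can escape AE and SAE reporting, but it remains in other collected data.
- **That a count can be given by applying a relapse rate to 200.** The 200 in Protocol 15.1 is the enrolment target. Cohort 1 takes tablets first, some subjects may never apply a patch, the safety population needs at least one application, and enrolment may stop early. No relapse rate is given, and no SAE rate either, so a comparison with other serious events has no basis.
- **That the expected early termination of about half of subjects measures relapse.** Protocol 15.1 gives no reasons for those terminations, which come from earlier tablet studies.

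What the reply does not remove is an explicit instruction not to report, with an undefined exception, that a site can apply in good faith to an admission.

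**Conclusion.** The concern holds in a narrow form. For worsening of schizophrenia symptoms already present that leads to an unplanned or prolonged hospitalisation, 12.1.1 supports two classifications, and nothing else in the protocol or SAP chooses between them. One leads to an SAE and a 24-hour report; the other leads to neither, and the event is missing from two of the SAP's TEAE summaries. The number of subjects affected cannot be derived from the documents. The conclusion rests on the text alone and needs no assumed rate.

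A reader might go further and infer that every worsening leading to rescue medication or discontinuation ought to be an AE. The documents do not require that. It is a debatable convention that would move much efficacy failure into the AE tables, and the gap shown here concerns serious events. Because safety is the primary objective and the correction is cheap, the change should be made.

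**What to change.** Reconcile the sentences in Protocol 12.1.1 with one recording rule:

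- Failure to improve is not an AE.
- Worsening of schizophrenia relative to the start of the current treatment period that meets a 12.1.2 seriousness criterion, for example unplanned or prolonged hospitalisation, is recorded as an AE and reported as an SAE. This applies even when the termination reason under 13.1 is lack of efficacy.

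Before database lock, run a programmed check that lists lack-of-efficacy terminations and rescue-antipsychotic records with no matching AE, and query the sites to confirm that no such event was missed. The data are already collected, and SAP sections 6 and 9.3 already plan a pre-lock review, so this part remains possible after enrolment has closed.

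The cost is a protocol wording change, a letter to sites, one check and a small amount of query work. AE and SAE counts will rise somewhat. The rule governs recording only and does not alter treatment.

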12.1.2 Serious adverse events

A serious adverse event (SAE) is an AE that meets one or more of the following criteria:

- Results in death.

- Is life-threatening (ie, a subject is at immediate risk of death at the time of the event, not an event where occurrence in a more severe form might have caused death).
- Requires hospitalization or prolongation of existing hospitalization.
- Results in persistent or significant disability or incapacity.
- Is a congenital anomaly or birth defect.
- Is an important medical event that may jeopardize the subject or may require a medical or surgical intervention to prevent one of the outcomes listed above. Examples of such medical events include allergic bronchospasm requiring intensive treatment in an emergency room or at home, blood dyscrasias or convulsions that do not result in inpatient hospitalization.

The term "severe" is often used to describe the severity of a specific event (as in mild, moderate, or severe myocardial infarction) (see Section 12.3); the event itself, however, may be of relatively minor medical significance (such as severe headache). This is not the same as "serious," which is based on subject/event outcome or action criteria usually associated with events that pose a threat to a subject's life or functioning as defined by the criteria above.

During the study, if a subject has a hospitalization or procedure that was scheduled before the study entry, ie, before informed consent for an event/condition that occurred before the study, the hospitalization is considered a therapeutic intervention and not the result of a SAE. However, if the event/condition worsens during the study, it should be reported as an AE (or SAE, if the event/condition results in a serious outcome such as prolongation of hospitalization).

12.2 Objective Findings

Clinically significant abnormal objective findings (eg, clinical laboratory value, ECG value, and physical examination observation) will also be recorded as AEs. When a clear diagnosis is available that explains the objective findings, this diagnosis will be recorded as the AE, and not the abnormal objective finding (eg, viral hepatitis will be recorded as the AE, not transaminase elevation). If a definite diagnosis is not available, then record the sign (eg, clinically significant elevation of transaminase levels) or symptom (eg, abdominal pain) as the AE.

Clinical laboratory test results will be reviewed by the Investigator. The Investigator must determine the clinical significance of all out of range values. Clinical laboratory test with possibly drug-related or clinically relevant abnormal values of uncertain causality may be repeated. Any abnormal values that persist should be followed at the discretion of the Investigator. Laboratory reports will be initialed and dated by the Investigator.

All ECG tracings at the study center and ECG over-read reports by the central ECG reader will be reviewed by the Investigator. The Investigator must determine the clinical significance of all

abnormal ECGs. An ECG with possibly drug-related or clinically relevant abnormal findings of uncertain causality may be repeated. Any abnormal ECGs that persist should be followed at the discretion of the Investigator. ECG tracings will be initialed and dated by the Investigator.

12.3 Collection and Recording of adverse events

All AEs will be, in principle, followed up until resolution, stabilization of the condition, the event is otherwise explained, or the subject is lost to follow-up. All AEs must be collected and recorded in the subject's study records/source documents, in accordance with the Investigator's normal clinical practice. AEs will be recorded in the CRFs from the beginning of the study treatment in the washout phase until the follow-up visit.

Each AE is to be evaluated for duration, severity, seriousness, action taken with the study treatment, outcome, and causal relationship to the study treatment. If any AEs related to skin disorders occur at the application site, the Investigator will record the location (the back, chest or abdomen) of AEs occurrence.

Definitions for severity, action taken with the study treatment, outcome, and causal relationship to the study treatment are presented below.

The severity of AE:

- Mild – Ordinarily transient symptoms that do not influence performance of subject's daily activities. Other treatment is not ordinarily indicated.
- Moderate – Marked symptoms sufficient to make the subject uncomfortable. Moderate influence on performance of subject's daily activities. Other treatment may be necessary.
- Severe – Symptoms cause considerable discomfort. Substantial influence on subject's daily activities. May be unable to continue the study, and other treatment may be necessary.

The action taken with the study treatment:

- Drug Withdrawn – Study drug stopped permanently.
- Dose Reduced.
- Dose Increased.
- Dose Not Changed.
- Not Applicable.
-

The outcome of the AE:

- Recovered/Resolved.
- Recovering/Resolving.

- Not Recovered/Not Resolved.
- Recovered/Resolved with Sequelae.
- Fatal.
- Unknown.

The causal relationship of the AE to the study treatment:

Not related

- Not related – Improbable temporal relationship and is plausibly related to other drugs or underlying disease.

Related

- Possible – occurred in a reasonable time after study drug administration (application), but could be related to concurrent drugs or underlying disease.
- Probable – occurred in a reasonable time after study drug administration (application), is unlikely to be attributable to concurrent drugs or underlying disease, and there is a plausible mechanism to implicate the study drug.
- Definite – occurred in a reasonable time after study drug administration (application) and cannot be explained by concurrent drugs or underlying disease. The adverse event should respond to dechallenge/rechallenge, however, this is not mandatory before assigning a definite causality.

The Sponsor is the contact person. The contact information as well as other emergency contact information can be found in Table 1 Emergency Contact Information.

12.4 Immediately Reportable Events

The following medical events must be immediately reported to the Sponsor:

- SAE
- Pregnancy

Emergency contact information can be found in Table 1 Emergency Contact Information.

12.4.1 Serious adverse event

If the Investigator or staff of study centers becomes aware of SAE that occurs in a study subject from the beginning of the DSP-5423 (tablet) administration until the follow-up visit in the cohort 1, or from the beginning of the DSP-5423P application until the follow-up visit in the cohort 2, this must be reported immediately to the Sponsor whether considered related or unrelated to the study drug. SAEs occurring during above period must be recorded in the CRFs.

Following the end of subject participation in the study, the Investigator should report SAEs “spontaneously” to the Sponsor if considered at least possibly related to the study drug.

SAEs will be followed until resolution, loss to follow-up, stabilization of condition, or the event is otherwise explained.

The Investigator must inform the Sponsor (Table 1 Emergency Contact Information) of any SAEs that occur during the course of the study within 24 hours of the Investigator becoming aware of the SAE. The SAE report should include the following information;

- History of any ADRs, relevant special conditions of the subject, history of the current disease and treatment for the disease, details of the SAE, treatment for the SAE and details on course of the SAE
- If the subject died, date of death, cause of death, relationship between the SAE and death, anatomic findings (if available)

These SAEs must be promptly reported in writing to the head of the study center by the Principal Investigator. The Principal Investigator should report available information in writing after the first reporting (this procedure is not mandatory in the case that the Principal Investigator has already submitted the first report, including all necessary information listed above). The Principal Investigator should report other necessary information not included in the first and second reports in writing as it becomes available.

The Sponsor will promptly notify all study centers and Investigators of a SAE that is determined to be expedited to the Regulatory Authority in accordance with applicable law(s) and regulation(s).

12.4.2 Pregnancy

Pregnancies that occur from the beginning of the DSP-5423 (tablet) administration until the follow-up visit in the cohort 1, or from the beginning of the DSP-5423P application until the follow-up visit in the cohort 2 will be collected and reported to the Sponsor.

If a subject becomes pregnant during the above period, she will be instructed to commence discontinuation of the study medication. Further, the subject (or female partner of a male subject) will be instructed to return promptly after the first notification of pregnancy to the study center and undergo a serum pregnancy test, as confirmation of pregnancy. If positive, the subject will no longer receive any additional study medication. All pregnancies will be followed until resolution (ie, termination [voluntary or spontaneous] or birth).

If the Investigator becomes aware of pregnancies, this must be promptly reported directly or by telephone or facsimile to the Sponsor. The Investigator must complete the Pregnancy Event Form and send it to the Sponsor.

Pregnancy itself is not regarded as an AE unless there is a suspicion that the study drug may have interfered with the effectiveness of a contraceptive medication or other AEs were detected.

